13.3.3 Relationship between Neurocognitive Scores, Blood Phe, and Prescribed Dietary Phe

The relationship between components of the WPPSI-III or WISC-IV and blood Phe will be examined. Specifically,

- 1) Observed values in FSIQ and observed values in blood Phe at end of study
- 2) Observed values in other components and observed values in blood Phe at end of study
- 3) Change in FSIQ and change in blood Phe at end of study
- 4) Change in other components and change in blood Phe at end of study
- 5) Observed values in FSIQ and observed values in prescribed dietary Phe at end of study
- 6) Observed values in other components and observed values in prescribed dietary Phe at end of study
- 7) Change in FSIQ and change in prescribed dietary Phe at end of study
- 8) Change in other components and change in prescribed dietary Phe at end of study

	SAP PKU-015, Version 3.0	Page 25 of 31
---	--------------------------	---------------

- 9) Change in FSIQ at end of study and SD of blood Phe over the study period
- 10) Change in other components at end of study and SD of blood Phe over the study period

For the above analyses, each subject's final assessment should occur within the same visit. Because each subject will have a different duration, study duration will be summarized as well. For items 9 and 10 above, these analyses will be repeated for subjects with assessments at Month 60 and at least one additional assessment after Month 60. In this analysis, the changes are calculated from Month 60, not Baseline.

Scatterplots will be presented and correlation calculated for each analysis.

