4 GENERAL ANALYSIS CONSIDERATION

Continuous endpoints will be summarized using descriptive statistics such as the number of observations, mean, standard deviation, median, minimum, maximum, 25th percentile, and 75th percentile. Categorical endpoints will be summarized by the frequency and percent.

The last available measurement or procedure performed prior to initial study drug administration will be considered the baseline measurement or procedure for analysis purpose, unless otherwise specified.

All tests will be conducted at a two-sided alpha level of 0.05, and all confidence intervals will be given at a two-sided 95% level, unless stated otherwise.

No multiplicity adjustment will be made. Data from all sites will be pooled; no by-site analysis will be performed.

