13.3 Exploratory analyses

Exploratory variables include:

- IQ scores
- Blood Phe concentration
- Relationship between neurocognitive testing and blood Phe
- Prescribed dietary Phe

A subject listing of IQ scores, neurocognitive testing results, blood Phe, and prescribed dietary Phe will be provided.

	SAP PKU-015, Version 3.0	Page 23 of 31
---	--------------------------	---------------

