13.3.2 Blood Phe Concentration

The observed value and change from Baseline in blood Phe will be summarized at each scheduled visit and across all visits. In addition, the average proportion of Phe values between the target range of 120 and 360 across each subject will be presented.

Another measurement of interest is the Index of Dietary Control (IDC), defined as half-year Phe level medians averaged over the first 6 months, over the first year, and annually thereafter. Descriptive statistics of the IDC will be produced.

Figures displaying mean change in Phe from baseline and IDC at each time point will be produced.

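### Items 9 and 10 of SAP Section 13.3.3 correlate IQ change with the raw SD of blood Phe without adjusting for mean Phe, so an effect of Phe level alone can look like an effect of fluctuation

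*SAP*

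**What the plan says.** SAP Section 13.3 lists "Relationship between neurocognitive testing and blood Phe" among the exploratory variables. Section 13.3.3 then sets out ten pairings. Two of them use the spread of blood Phe instead of a Phe value: item 9, "Change in FSIQ at end of study and SD of blood Phe over the study period", and item 10, "Change in other components at end of study and SD of blood Phe over the study period". The method for all ten is one sentence: "Scatterplots will be presented and correlation calculated for each analysis".

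Items 9 and 10 are repeated in children assessed at Month 60 and at least once later. The stated difference from the main analysis, apart from the subset, is the starting point: "In this analysis, the changes are calculated from Month 60, not Baseline".

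The other Phe pairings (items 1 to 4) use the end-of-study value or its change, for example "Change in FSIQ and change in blood Phe at end of study". Section 13.3.2 defines a long-term measure of Phe level, the Index of Dietary Control (IDC), but only describes it: "Descriptive statistics of the IDC will be produced".

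**The concern.** Blood Phe is a positive concentration. For such a quantity the SD within a child often rises with that child's mean, so a poorly controlled child tends to have both a high average and a large SD. A simple correlation of IQ change with the SD then carries whatever association IQ change has with the average. Because the plan has no analysis of IQ change against average Phe, a reader who sees a negative correlation in item 9 or 10 has nothing in the planned output to show whether fluctuation or level lies behind it.

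What is at stake is interpretation: a statement in the study report about unstable Phe that the data may not support.

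**Working it through.** **1. The plan's own figure.** Section 13.3.3 gives no number. The sample size section (3.4) supplies n = 45. Its power claim reproduces: SD of change = 16 × √(2 × (1 − 0.8)) = 10.12; standard error = 10.12/√45 = 1.51; 5/1.51 = 3.31; 3.31 − 1.96 = 1.35; normal power 91.2%, noncentral t 90.0%, against the stated 90%. It has no bearing on items 9 and 10 beyond the 45.

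**2. Is level dealt with elsewhere?**
- Items 1 to 4: Phe at the end of the study, or its change. Not the average.
- Items 5 to 8: prescribed dietary Phe.
- Section 13.3.1: repeated measures model for FSIQ with visit and testing sequence as factors; no Phe term.
- Section 13.3.2: Phe by visit, across visits and as IDC; descriptive only.

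None relates IQ change to average Phe.

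**3. Expected size.** If IQ change depends on mean Phe only, then approximately

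corr(SD, IQ change) ≈ corr(SD, mean) × corr(mean, IQ change).

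With corr(SD, mean) = 0.75 and level–IQ correlations of -0.3 and -0.5 this gives 0.75 × -0.3 = -0.23 and 0.75 × -0.5 = -0.38. With 45 children, |r| is significant at two-sided 5% from 2.017/√(43 + 2.017²) = 0.29.

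**4. Simulation.** Every Phe input is an assumption, because the SAP gives none. 3000 trials; 45 children, 20 gamma-distributed Phe values each; child means lognormal around 300 with between-child CV 30%; within-child CV 40% with 20% random scatter in the SD from child to child. IQ change depends on the child's true mean and not on the SD.

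| SD across children | Level–IQ corr. | corr(SD, mean) | Raw corr. SD–IQ | Raw p<0.05 | Partial corr. | Partial p<0.05 | CV p<0.05 |
|---|---|---|---|---|---|---|---|
| Proportional to mean | -0.3 | 0.75 | -0.21 | 28% | 0.00 | 5% | 5% |
| Proportional to mean | -0.5 | 0.75 | -0.35 | 67% | 0.01 | 5% | 5% |
| Proportional to √mean | -0.3 | 0.53 | -0.14 | 16% | 0.02 | 5% | 14% |
| Proportional to √mean | -0.5 | 0.53 | -0.23 | 33% | 0.03 | 6% | 33% |
| Unrelated to mean | -0.3 | 0.13 | -0.01 | 5% | 0.03 | 6% | 28% |
| Unrelated to mean | -0.5 | 0.13 | -0.01 | 5% | 0.06 | 7% | 63% |

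The simulated raw correlations are a little smaller than the product in step 3. The sampled SD and mean of the same skewed values share sampling error, which raises their correlation but has nothing to do with IQ.

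**5. Wider range of spread.** With level–IQ correlation -0.3 to -0.4, between-child CV 20–50% and within-child CV 40%, the raw correlation is significant in about 14–68% of studies when SD rises with the mean and about 5% when it does not. After adjustment for mean Phe it is 4–7%.

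**6. More children do not help.** In the second row, 60 children instead of 45 raise 67% to 79%.

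**7. The coefficient of variation is not a remedy.** It removes the artefact only when SD is exactly proportional to the mean. Otherwise it gives a spurious correlation of the opposite sign, significant in 14–63% of trials in the table.

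**8. Price of adjusting.** The variance of the SD slope is inflated by 1/(1 − r²), where r = corr(SD, mean). At 0.75: 1/(1 − 0.5625) = 2.3, or 45/2.3 ≈ 20 children's worth of information. At 0.84 and 0.93: 3.4 and 7.4, or about 13 and 6.

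**The case against.** The strongest reply is that the SAP never asks whether fluctuation matters beyond level. Section 13.3.3 says only that relationships will be examined, and a marginal correlation does describe a marginal relationship. That stands: a reader might infer that items 9 and 10 fail at a question the plan sets itself, but no such question is written down. Reading them as analyses of fluctuation is natural, since they are the only IQ pairings that use spread, but it is a reading.

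Second, a reader might infer that a level effect *will* show up as a fluctuation effect. The documents do not support that. It needs SD to rise with the mean across these children, and mean Phe to be related to IQ change. Neither is shown. Eligibility (controlled Phe at entry, at least a 30% reduction for Part 2) and the provision for dietary adjustment could narrow the spread of child means, which weakens the artefact. If SD is unrelated to the mean, it vanishes.

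Third, Section 13.3.3 names no p-value for these correlations, whereas Section 13.3.1 does where one is wanted. Section 4 ("All tests will be conducted at a two-sided alpha level of 0.05") sets the level for tests that are done. The significance percentages are therefore a yardstick; the raw correlations in the table measure the distortion directly.

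Fourth, if poor control drives both level and swings, holding the mean fixed changes the quantity being estimated. That is a reason to show both correlations, not to omit the adjusted one.

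**Conclusion.** The point holds in conditional form. As planned, items 9 and 10 and their Month 60 repeat cannot separate fluctuation from level, and nothing else in the SAP fills the gap. If SD rises with the mean, an effect of level alone produces a raw SD–IQ correlation of about -0.14 to -0.35 in the tabulated settings, and a significant one in about 14–68% of studies over the range in step 5, against about 5% if SD and mean are unrelated. These sizes rest wholly on assumed Phe spread, number of Phe values and level–IQ correlation; only the 45 children and the 5% level come from the SAP.

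Severity is CONSIDER. The analysis is exploratory, no success criterion depends on it, and the primary, supportive and secondary analyses and the sample size are unaffected.

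**What to change.** Add to Section 13.3.3, for items 9 and 10 and their repeat from Month 60: *Beside the unadjusted correlation, the partial correlation of IQ change with the SD of blood Phe, adjusted for the child's mean blood Phe over the same values, will be reported with a 95% confidence interval, together with the correlation between SD and mean.* Do not add the coefficient of variation, either as a substitute or as an extra column.

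The cost is a sentence in the SAP, a little more output from Phe values already collected, and one degree of freedom. The real downside is precision. Where SD and mean are highly correlated, little variation in SD is left once the mean is held fixed, and more so in the smaller Month 60 subset. Even a real effect of fluctuation would then give only a small partial correlation. The SAP should say that a null partial result is inconclusive in that case; the SD–mean correlation shows the reader when it applies.

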13.3.4 Prescribed Dietary Phe

The observed value and change from Baseline in prescribed dietary Phe will be assessed at each scheduled visit.

In addition, the relationship between the change in z-score weight and height will be examined alongside the change in prescribed dietary Phe. The final assessment of weight, height, and dietary Phe should occur within the same visit. Scatterplots will be presented and correlation calculated for each analysis.

	SAP PKU-015, Version 3.0	Page 26 of 31
---	--------------------------	---------------

14 SAFETY EVALUATIONS

Safety will be assessed by examining the incidence, severity grade, and relationship to study drug of all treatment-emergent adverse events (TEAEs) reported during the study period. In addition, clinical laboratory results, vital signs, ECG, and physical exam will be assessed. No formal statistical testing will be performed for the safety analyses; only descriptive statistics will be provided. Safety summaries will be presented for the Safety population using both group presentations as described in Section 4.2 unless noted otherwise.

14.1 Adverse Events

14.1.1 All Adverse Events

Adverse events will be coded in accordance with the most current version of MedDRA at program termination or annual reporting. Only treatment-emergent adverse events (TEAEs) occurring and reported during the study will be included in the adverse event summaries. A TEAE is defined as any AE that newly appeared or worsened in severity following initiation of the study drug administration. If the onset date of an AE is missing, the AE will be considered treatment-emergent. The incidence of all treatment-emergent AEs will be summarized by system organ class (SOC), preferred term (PT), relationship to study drug and CTCAE grades. For those AEs that occurred more than once, regardless of study part, the maximum severity will be used to summarize the AEs by severity.

If the onset date or end date of an adverse event is partial, the same imputation rules described in section 9 will be applied.

The treatment-emergent AEs will be summarized in the following categories:

- All AEs by SOC and preferred term
- All AEs by preferred term in descending frequency order
- All AEs by SOC, preferred term, and NCI CTCAE grade
- AEs assessed by investigators as related to study drug by SOC and preferred term
- AEs assessed by investigators as related to study drug by SOC, preferred term and NCI CTCAE grade
- Serious AEs (SAEs) by SOC and preferred term
- All SAEs by preferred term in descending frequency order

	SAP PKU-015, Version 3.0	Page 27 of 31
---	--------------------------	---------------

- SAEs assessed by investigators as related to study drug by SOC and preferred term
- Death
- AEs leading to withdrawal from study by SOC and preferred term
- AEs leading to study drug discontinuation by SOC and preferred term

A summary of all AEs and adverse event listings will also be provided.

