3.2 Study Design

This 2-part, multicenter, open-label study is designed to evaluate the safety of Kuvan and its effect on neurocognitive function, blood Phe concentration, and growth in children with PKU when treatment is initiated at 0-6 years of age. The study will be considered complete when approximately 45 subjects have completed 7 years of treatment.

One of the goals of the study will be to decrease blood Phe levels to reach a goal of ≤ 240 $\mu\text{mol/L}$. Subjects will meet with a dietician at each study visit to review dietary Phe intake. Dietary Phe may be added to the diet, at the discretion of the Investigator, if a blood Phe level falls below 120 $\mu\text{mol/L}$ or decreased if blood Phe level is above 240 $\mu\text{mol/L}$. If a subject's blood Phe falls below 120 $\mu\text{mol/L}$, at the discretion of the investigator, a gradual increase of approximately 5-20 mg/kg of Phe supplement may be added to the diet. If a subject's blood Phe level goes above 240 $\mu\text{mol/L}$, dietary Phe may be decreased by

	SAP PKU-015, Version 3.0	Page 7 of 31
---	--------------------------	--------------

approximately 5 to 20 mg/kg or defined by the standard used at each treatment center, at the discretion of the investigator.

Part 1: Evaluation of Kuvan Responsiveness

Beginning at Week 0 and after all baseline assessments are completed, subjects enrolled into the study will receive 20 mg/kg Kuvan daily for 4 weeks. Subjects will return to the clinic weekly for safety assessments and blood Phe concentration measurement. Subjects should continue with their current amount of dietary Phe intake. However, if a subject's blood Phe concentration drops below 120 $\mu\text{mol/L}$, at the discretion of the Investigator, a gradual increase by approximately 5 to 20 mg/kg of daily dietary Phe supplement may be added to the diet. It is important to avoid unstable swings in blood Phe concentrations. No dose adjustments can be made during Part 1 without consultation with the Medical Monitor.

Part 2: Neurocognitive Study

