3.4 Sample Size Determination

The sample size calculation assumes each child will have 2 post-treatment test results from the WPPSI-III and /or WISC-IV tests at least 2 years apart. The goal is to exclude a mean 2.5-point loss per year in IQ score. Given a 2-side Type I error rate of 0.05, if the mean IQ score at baseline is 100, the standard deviation is no larger than 16, and the correlation between the 2 test results is 0.8, a sample size of 45 subjects will yield at least 90% power.

To account for the possibility of dropouts and to have reasonable precision for estimating change in IQ from the time a child reaches at least age 30 months until the end of the study, approximately 60-80 Kuvan-responsive subjects will be enrolled in the study.

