4.1 Analysis Populations

The Full Analysis set (FAS) will consist of all subjects who enroll into the study.

The Enrolled population will consist of all subjects who enter Part 2 of the study and met the inclusion/exclusion criteria per CRF. This population involves subjects who respond to Kuvan and had a Bayley-III or IQ test score ≥ 80 within 6 weeks of determination of Kuvan responsiveness in Part 1. Kuvan responders consist of all subjects with at least 30% average reduction in blood Phe concentration calculated as the mean of the weekly percent change from baseline at Week 1, 2, 3 and 4 in Part 1.

The Efficacy population will consist of all subjects from the Enrolled population who have at least two WPSI/WISC assessments.

The Safety population will consist of all subjects who have received any study drug in the FAS population.

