14.1.2 Adverse Events of Special Interest

Occurrences of AEOsIs are derived based on the search strategy below. AEOsIs will be summarized in a similar manner to general adverse events for any and each AEOsI and listed as well. Only summaries involving Part 2 subjects are examined.

In addition, the exposure-adjusted incidence rate for each AEOsI will be summarized. This rate will be calculated as the number of individuals with the event starting at first study drug administration, divided by the total number of patient-years at risk for the event, multiplied by 100. In calculating patient-years at risk for a given event, the follow-up time for a patient experiencing that event will conclude at the event start date. If the subject never experience the event, the subject will be censored at the discontinuation visit, death, or last follow-up visit, whichever is earlier. Mean cumulative function plots will also be produced for any AEOsI if the number of events for that specific AEOsI are sufficient.

The following adverse events are of interest:

TERM	STRATEGY
hypophenylalanenemia	MedDRA Preferred Terms(PTs): Phenylketonuria, Amino acid level decreased and Amino acid level abnormal
convulsions	Standardised MedDRA queries(SMQs): Convulsions
epigastric ulcer	Standardised MedDRA queries(SMQs): Gastrointestinal ulceration, Gastrointestinal perforation and Gastrointestinal haemorrhage
nephrotoxicity	Standardised MedDRA queries(SMQs) of Broad acute renal failure, Broad chronic kidney disease or MedDRA HLGT Term(s) of Nephropathies and Renal disorders (excl nephropathies)
behavioural changes	MedDRA HLGT Term(s): Behaviour and socialisation disturbances

	SAP PKU-015, Version 3.0	Page 28 of 31
---	--------------------------	---------------

TERM	STRATEGY
nephrolithiasis	MedDRA HLGT Term(s): Renal lithiasis
GERD	MedDRA Preferred Terms(PTs): Gastroesophageal reflux disease, Barrett’s esophagus, and Gastrointestinal nonspecific inflammation and dysfunctional disorders
Hypersensitivity Reactions	Standardized MedDRA Queries(SMQs): Broad Hypersensitivity reaction
Anaphylactic reaction - Broad Algorithmic anaphylactic reaction SMQ	Standardized MedDRA Queries(SMQs): Broad algorithmic anaphylactic reaction
New onset anxiety disorders	MedDRA HLGT Term(s): Anxiety disorders and symptoms
Worsening of psychiatric disorders	MedDRA System Organ Class (SOC): Psychiatric disorders
Drug-drug interaction	MedDRA PTs: Phenylketonuria and Neurotransmitter level altered

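### General adverse event tables give only crude incidence over very unequal follow-up, so percentages and age-group contrasts depend on retention; the all-ages denominator is also contradictory

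*SAP*

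**What the plan says.** Section 14.1.1 of the SAP sets the measure for general treatment-emergent adverse events (TEAEs): "The incidence of all treatment-emergent AEs will be summarized by system organ class (SOC), preferred term (PT", and likewise by drug relationship and severity grade. The tables that follow from it cover all AEs, drug-related AEs, serious AEs (SAEs), and AEs leading to study withdrawal or drug discontinuation. Section 4 makes frequency and percent the default for categorical data.

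Section 14.1.2 treats adverse events of special interest (AEoSIs) differently. They are first summarised like general AEs, and then: "In addition, the exposure-adjusted incidence rate for each AEOsI will be summarized". That rate is children with the event per 100 patient-years at risk, with follow-up ending at the first event. The section adds a restriction: "Only summaries involving Part 2 subjects are examined".

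On exposure, Part 1 gives 4 weeks of drug (Section 3.2). Section 3.2 also says "The study will be considered complete when approximately 45 subjects have completed 7 years of treatment", and Section 3.4 says "approximately 60-80 Kuvan-responsive subjects will be enrolled in the study".

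On who is counted, Section 4.1 says "The Safety population will consist of all subjects who have received any study drug in the FAS population", and Section 14 presents safety for that population using both groupings of Section 4.2. The first grouping, by age, is defined for children enrolled in Part 2. The second, which splits Part 1 results into Part 2 enrolled, not enrolled and overall, is one that may be presented.

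**The concern.** Long-term safety is a secondary objective (Section 3.1). A percentage of children with an event is a risk over a stated period only if the children were followed for that period. Here some Part 2 children will have 7 years or more and others much less. A group that loses children early has less time in which to record events, so with the same underlying rate it shows a lower percentage. Because the tables are split by age group, a difference in retention can look like a difference in safety between ages.

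The SAP recognises the problem for AEoSIs and defines a suitable rate there. The overall totals for SAEs, related TEAEs and discontinuations, and most system organ classes (SOCs), do not get it.

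A second issue is the denominator. Two programmers reading Sections 4.1, 4.2 and 14 could reasonably produce different all-ages columns, one with and one without the children who were dosed only in Part 1.

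**Working it through.** **Is the 14.1.1 summary unadjusted?** The SAP says incidence, not crude incidence. Section 14.1.2 settles the reading: AEoSIs are summarised as general AEs are, and the exposure-adjusted rate comes in addition. The general summary is therefore n and %.

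The SAP gives no expected AE percentage to reproduce, so what follows is an illustration.

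**Inputs from the SAP.** 45 children with 7 years; 60 to 80 responders; 4 weeks in Part 1 (28/365.25 = 0.077 year). By subtraction, 60 - 45 = 15 to 80 - 45 = 35 responders have less than 7 years.

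**Assumed inputs.** Constant event rate λ = 0.05 per year (5 per 100 patient-years). Non-completers' follow-up spread evenly over 0.1 to 7 years. All 60-80 responders counted as Part 2 children, which is a simplification because Part 2 also requires a score of at least 80. The number of Part 1-only children is not given; 0, 20 and 40 are tried.

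**Formulas.** Probability of at least one event by time t: p(t) = 1 - exp(-λt).

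- p(0.077) = 0.4%
- p(1) = 4.9%
- p(3.5) = 16.1%
- p(7) = 29.5%

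Average over follow-up spread evenly on 0.1 to 7 years: u = 1 - [exp(-0.005) - exp(-0.35)] / (0.05 × 6.9) = 15.8%.

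**Part 2 children only.**

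| Part 2 children | Completers | Non-completers' follow-up | Crude incidence |
|---|---|---|---|
| any | all | none | 29.5% |
| 60 | 45 | even, 0.1-7 y | (45 × 0.2953 + 15 × 0.1585)/60 = 26.1% |
| 80 | 45 | even, 0.1-7 y | (45 × 0.2953 + 35 × 0.1585)/80 = 23.5% |
| 60 | 45 | 1 y each | (45 × 0.2953 + 15 × 0.0488)/60 = 23.4% |
| 80 | 45 | 1 y each | (45 × 0.2953 + 35 × 0.0488)/80 = 18.7% |

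An age group with only 40% completing would show 0.4 × 29.5% + 0.6 × 15.8% = 21.3%. The true rate is the same in every row.

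**If Part 1-only children were in the denominator** (even spread for non-completers):

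| Part 1-only children (assumed) | 60 responders | 80 responders |
|---|---|---|
| 0 | 26.1% | 23.5% |
| 20 | 19.7% | 18.9% |
| 40 | 15.8% | 15.8% |

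Forty such children add only 40 × 0.077 = 3.1 patient-years to a total of 45 × 7 + 15 × 3.55 = 368 (60 responders) or 45 × 7 + 35 × 3.55 = 439 (80 responders). They would change the percentage a good deal and a rate per patient-year hardly at all.

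**Which denominator does the text give?** Towards all dosed children: the Safety population in Section 4.1, its use in Section 14, and the express Part 2 restriction in Section 14.1.2, which would be redundant if Section 14.1.1 were already so restricted. Towards Part 2 children only: Section 4.2 defines the age groups for Part 2 enrollees and foresees a separate display for Part 1. The text does not resolve this.

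**The case against.** The strongest case against has five parts.

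- **Part 1-only children.** A reader might infer that the tables will be diluted by children with 4 weeks of exposure. The documents do not establish this. As written, Section 4.2 puts Part 2 children in the age-group columns, and its Part 1 display compares enrolled and not-enrolled children over a common period of about 4 weeks. This objection stands: dilution is one possible reading of a contradiction, not a fact.
- **Size.** A reader might call the spread nearly two-fold. It is not: 26.1% against 15.8% is a ratio of 1.65 (23.5% against 15.8% is 1.49), and that needs 40 Part 1-only children, an assumed number. Among Part 2 children alone, the even-spread model gives 26.1% against 23.5%. That the rate stays at 5 per 100 patient-years is the assumption itself, not a result about this trial.
- **Scope.** It is not true that no TEAE gets a rate. AEoSIs do, and they include the whole Psychiatric disorders SOC and broad hypersensitivity and renal searches. Only what falls outside them is affected.
- **Exposure is reported.** Section 12 summarises duration by age group, study part and overall. This helps a reader judge follow-up, but patient-years at risk for a first event cannot be derived from it.
- **No decision hangs on it.** The study is single-arm and safety is descriptive, so no test or treatment comparison is affected. That limits the weight of the point. It does not make the percentages interpretable as long-term risks.

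A technical caution also stands: for any TEAE, a first-event rate says little if most children have an event early.

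**Conclusion.** The point holds in a limited form. The general TEAE, related-AE, SAE and discontinuation tables have no exposure adjustment, while follow-up within Part 2 is planned to be very unequal, so the percentages and age-group contrasts depend on retention. Under the stated assumptions the same true rate gives crude figures from 29.5% down to about 19% among Part 2 children alone. The all-ages denominator is a separate, unresolved contradiction; only if Part 1-only children were counted would the figure fall further, to about 16% with 40 of them.

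The event rate, dropout times and number of Part 1-only children are all assumptions, and the SAP does not allow the actual size or direction of any age-group distortion to be fixed. This is an inexpensive improvement to reporting on a secondary objective. It does not touch the primary analysis.

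**What to change.** In Section 14.1.1, keep the crude n (%) and add beside it:

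- the Section 14.1.2 rate (children with a first event per 100 patient-years at risk), with 95% CI, for any SAE, any related TEAE, any TEAE leading to discontinuation, and each SOC;
- for any TEAE, total events per 100 patient-years, because first events come early.

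In Sections 4.2 and 14, state that the age-group and all-ages AE tables use Part 2 enrollees. Make the Part 1 display (Part 2 enrolled, not enrolled, overall) firm rather than optional, so that every dosed child is covered over a common period. Show N and total patient-years in each column head.

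This needs SAP wording only and no new data, since the rate, its at-risk time and its censoring are already defined for AEoSIs. The cost is additional table columns. A single rate also assumes a roughly constant hazard, which should be said where the rates are presented.
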